2.3.1.2 Durvalumab + chemotherapy

Studies evaluating agents targeting PD-L1 in combination with chemotherapy have yielded encouraging results.

CASPIAN is a randomised, open-label, multi-centre, global, Phase III trial in the first line treatment of 805 patients with ES-SCLC. The trial compared durvalumab in combination with etoposide and either carboplatin or cisplatin chemotherapy, or durvalumab and chemotherapy with the addition of a second immunotherapy, tremelimumab, versus chemotherapy alone. In the experimental arms, patients were treated with four cycles of chemotherapy. In comparison, the control arm allowed up to six cycles of chemotherapy and optional prophylactic cranial irradiation. The trial was conducted in more than 200 centres across 23 countries.

Durvalumab plus platinum–etoposide demonstrated a statistically significant and clinically meaningful improvement in overall survival versus platinum–etoposide alone, with an HR of 0.73 (95% CI 0.59–0.91; $p=0.0047$) (Paz-Ares 2019). Median overall survival was 13.0 months (95% CI 11.5–14.8) with durvalumab plus platinum– etoposide versus 10.3 months (9.3–11.2) with platinum– etoposide; the 12-month overall survival rates were 54% (47.4–59.5) versus 40% (33.7–45.8); and the 18-month overall survival rates were 34% (26.9–41.0) versus 25% (18.4–31.6). Overall survival benefit was observed across all clinically relevant patient subgroups. Consistent with the results for overall survival, progression-free survival (assessed without

formal statistical significance testing) was also in favour of durvalumab plus platinum–etoposide, as were objective response. Importantly, adding durvalumab to platinum-etoposide demonstrated significant and durable improvements in overall survival while maintaining quality of life, by delaying worsening of patient-reported symptoms, functioning, and HRQoL compared to platinum-etoposide alone.

Patients receiving durvalumab plus platinum–etoposide experienced reduced symptom burden over 12 months for pre-specified symptoms of fatigue, appetite loss, cough, dyspnea, and chest pain; a statistically significant difference over 12 months was observed for appetite loss in favor of durvalumab plus platinum–etoposide compared to platinum–etoposide alone. Patients in the durvalumab plus platinum–etoposide group experienced longer time to deterioration in a broad range of patient-reported symptoms, functioning and HRQoL compared to platinum–etoposide.

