9.5.2.3 Patient reported outcomes

Summary measures of visit and overall compliance and completion rates will be derived for each PRO questionnaire. Refer to the SAP for details.

For PRO symptoms and health related quality of life endpoints, the main concepts of interest have been identified using a literature review, and detailed qualitative interviews SCLC patient and clinicians. The key symptoms were: cough, hemoptysis, dyspnea, chest pain, insomnia, fatigue and appetite loss.

Therefore we would like to pre-specify that an effective treatment would reduce time to deterioration and effect mean change from baseline in these key SCLC symptoms. The prespecified symptomatic endpoints are as follows: time to deterioration from baseline of cough, hemoptysis, dyspnea and chest pain from EORTC QLQ- LC13; and insomnia, fatigue and appetite loss from EORTC QLQ -C30; as well as average mean change of the key symptoms.

In addition, physical functioning and overall health status domains of the EORTC QLQ-C30 are furthermore pre-specified endpoints of interest.

The detail how this data will be analysed and the effect we would like to see to determine a symptomatic treatment effect will further be detailed and pre-specified in the SAP.

(a) EORTC QLQ-C30

If possible, time to symptom deterioration will be summarized for each of the 3 symptom scales (fatigue, pain, nausea/vomiting) and the 5 individual symptom items (dyspnea, insomnia, appetite loss, constipation, diarrhea). Similarly, a summary of QoL/function deterioration will be summarized for each of the function scales (physical, role, emotional, cognitive, and social) and global health status/QoL. This will be achieved by using Kaplan-Meier product limit methods to provide summaries of the number and percentage of patients experiencing a clinically meaningful deterioration or death, the median time to deterioration together with the corresponding 95% CIs, as well as the Kaplan-Meier plots.

Summaries of original and change from baseline values of each symptom scale/item, the global HRQoL score, and each functional domain will be reported by visit. Details will provided in the SAP.

Definition of clinically meaningful changes

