For each of the symptoms scales/items in the EORTC QLQ-C30 questionnaire, time to symptom deterioration will be defined as the time from start of study drug until the date of the first clinically meaningful symptom deterioration (an increase in the score from baseline of ≥ 10 points) that is confirmed at the subsequent assessment (at least 14 days apart) or death (by any cause) in the absence of a clinically meaningful symptom deterioration, regardless of whether the patient withdraws from study drug or receives another anticancer therapy prior to symptom deterioration. Death will be included as an event only if the death occurs within 2 visits of the last PRO assessment where the symptom change could be evaluated.

Patients with a single deterioration and no further assessments will be treated as deteriorated in the analysis. Patients whose symptoms (as measured by EORTC QLQ-C30) have not shown a clinically meaningful deterioration and who are alive at the time of the analysis will be censored at the time of their last PRO assessment where the symptom could be evaluated. Also, if symptoms deteriorate after 2 or more missed PRO assessment visits or the patient dies after 2 or more missed PRO

assessment visits, the patient will be censored at the time of the last PRO assessment where the symptom could be evaluated. If a patient has no evaluable visits or does not have baseline data, he/she will be censored at Day 1.

The analysis of time to symptom deterioration will be done with a subset of patients who have baseline scores of ≤ 90 .

Time to quality of life/function deterioration

For QoL, time to deterioration will be defined as the time from start of study drug until the date of the first clinically meaningful deterioration (a decrease in the function scales or the global health status/QoL from baseline of ≥ 10 points) that is confirmed at the subsequent assessment (at least 14 days apart) or death (by any cause) in the absence of a clinically meaningful deterioration, regardless of whether the patient withdraws from study drug or receives another anticancer therapy prior to QoL/function deterioration. Death will be included as an event only if the death occurs within 2 visits of the last PRO assessment where the QoL/function change could be evaluated.

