Patients whose QoL (as measured by EORTC QLQ-C30) have not shown a clinically meaningful deterioration and who are alive at the time of the analysis will be censored at the time of their last PRO assessment where the QoL/function could be evaluated. Also, if QoL deteriorates after 2 or more missed PRO assessment visits or the patient dies after 2 or more missed PRO assessment visits, the patient will be censored at the time of the last PRO assessment where QoL/function could be evaluated. If a patient has no evaluable visits or does not have baseline data, he/she will be censored at Day 1.

Symptom improvement rate

The symptom improvement rate will be defined as the number (%) of patients with 2 consecutive assessments at least 14 days apart that show a clinically meaningful improvement (a decrease from baseline score ≥ 10 points for EORTC QLQ-C30 symptom scales/items) in that symptom from baseline.

Quality of life/function improvement rate

The QoL/function improvement rate will be defined as the number (%) of patients with 2 consecutive assessments at least 14 days apart that show a clinically meaningful improvement (an increase from baseline score ≥ 10 points for EORTC QLQ-C30 functional scales and global health status/QoL) in that scale from baseline.

(b) EORTC QLQ-LC13

Data will be summarized for each of the symptom items in EORTC QLQ-LC13 as outlined above for EORTC QLQ-C30.

Summaries of original and change from baseline values of each symptom (dyspnea, cough, hemoptysis, chest pain, arm/shoulder pain, and other pain) and each treatment-related side effect (sore mouth, dysphagia, peripheral neuropathy, and alopecia) will be reported by visit. Details will be provided in the SAP.

(c) **PRO-CTCAE**

PRO-CTCAE data will be presented using summaries and descriptive statistics. Further details will be provided in the SAP.

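### Protocol 9.5.2.3 states the direction of benefit for time to symptom deterioration the wrong way round, and the SAP does not supply the effect it was meant to specify

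*Protocol*

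**What the plan says.** Protocol 9.5.2.3 names the key symptoms and then pre-specifies that "an effective treatment would reduce time to deterioration" and would also act on the mean change in those symptoms. Seven time-to-deterioration endpoints follow: cough, hemoptysis, dyspnea and chest pain from the QLQ-LC13, and insomnia, fatigue and appetite loss from the QLQ-C30. The average mean change of the key symptoms is added. The section then says that "the effect we would like to see to determine a symptomatic treatment effect will further be detailed and pre-specified in the SAP".

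Further on, the same section defines time to symptom deterioration as "the time from start of study drug until the date of the first clinically meaningful symptom deterioration", where deterioration is a rise of at least 10 points confirmed at the next assessment. Death without deterioration also counts as an event. Protocol 9.4 defines the endpoint in the same terms.

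In its account of the pivotal study, Protocol 2.3.1.2 reports that durvalumab patients "experienced longer time to deterioration in a broad range of patient-reported symptoms, functioning and HRQoL", and describes quality of life as maintained "by delaying worsening of patient-reported symptoms, functioning, and HRQoL".

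SAP 5.2.2 sets a 10-point threshold for meaningful change in either direction, a repeated-measures model for five symptoms, and Kaplan-Meier, log-rank and Cox methods for time to deterioration. It does not say what direction or size of result would show a symptomatic effect.

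**The concern.** A pre-specification exists so that the reading of a result is fixed before the data are seen. Here the written reading contradicts both the endpoint's definition and the benefit that the protocol reports for the same kind of endpoint in the pivotal study. The document that was to complete the criterion leaves it as it stands.

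On its own this could pass as a slip that any reader would correct. It matters more because the direction of symptom scores is also reversed in two other places in these documents. When someone reconciles those places, the sentence in 9.5.2.3 is a natural reference for what was intended, and it points the wrong way.

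**Working it through.** The plan gives no figure for this criterion, so the check is of direction.

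**1. Direction from the definition.** The event is confirmed worsening or death, both unfavourable. With cumulative event hazard H(t), the event-free proportion is S(t) = exp(−H(t)). A treatment that helps lowers H(t), which raises S(t) and lengthens the median time. Benefit is a longer time.

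**2. Direction from the protocol's own usage.** Protocol 2.3.1.2 counts *longer* time and *delayed* worsening as benefit. This agrees with step 1 and contradicts 9.5.2.3.

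**3. What else states a direction.**

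| Place | Statement | Direction |
|---|---|---|
| 9.5.2.3, time to deterioration in the effective-treatment sentence | shorter under effective treatment | reversed |
| 9.5.2.3, mean change in the same sentence | an effect on mean change | none given |
| 9.5.2.3, symptom improvement rate | fall of at least 10 points | correct, patient level |
| 9.5.2.3, QoL/function improvement rate | rise of at least 10 points | correct, patient level |
| SAP 5.2.2 | 10-point threshold, models, tests | no effect sought |

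The correctly directed statements classify individual patients. For example, the symptom improvement rate counts patients whose consecutive assessments "show a clinically meaningful improvement (a decrease from baseline score" of at least 10 points). Only the effective-treatment sentence says what a treatment should do to an endpoint, and its one stated direction is wrong.

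**4. Dependence on the direction of the event.** Take QLQ-C30 appetite loss, a single item scored 1 to 4. SAP 4.2.2.2 scores symptoms as (RS − 1)/range × 100. I take range as 4 − 1 = 3, which gives the 0 to 100 scale that both documents state. A patient who moves from *a little* (2) to *quite a bit* (3) goes from (2 − 1)/3 × 100 = 33.3 to (3 − 1)/3 × 100 = 66.7, a rise of 33.3 points. Appetite loss is worse. The documents classify that change as follows:

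- Protocol 9.5.2.3, time-to-symptom-deterioration text: a rise of 10 or more is deterioration. Correct.
- Protocol 9.5.2.3, visit-response table (captioned Table 14), symptom row: a rise of 10 or more is improvement. Reversed.
- SAP 4.2.2.2: symptom deterioration is a fall of 10 or more, and symptom improvement is a rise. Reversed.
- SAP 5.2.2: higher symptom scores mean greater severity. This agrees with the first item and conflicts with the other two.

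A further pointer lies in Protocol 9.5.2.3, which limits the symptom analysis to baseline scores of 90 or below. On a 0 to 100 scale, 90 + 10 = 100 is the highest baseline from which a 10-point rise is possible, so that limit fits an event defined as a rise.

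If the SAP 4.2.2.2 event were used, the event would be symptom relief or death, and a shorter time could look favourable. The word *reduce* would then appear to support the faulty definition. Correcting that word while leaving SAP 4.2.2.2 as it is would pair a correct direction with a reversed event.

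**The case against.** The strongest reply is that this is an editorial slip. The sentence has no threshold, reference value or comparator. Protocol 6.2.1 describes a single-arm study, 9.1 says there is no formal hypothesis, and the synopsis calls all analyses descriptive. With nothing for the time to be shorter than, no result can formally meet or fail the sentence. The SAP does not repeat it, so it reaches no programmed output. SAP 5.2.2 does plan a log-rank test and hazard ratios, but they do not use the sentence. All of this stands, and it is why the point is minor.

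Two stronger readings are tempting, and the documents support neither. A reader might infer that the reversed sentence is the protocol's only criterion for patient-reported benefit. It is not: the same sentence also names mean change, and the text of 9.5.2.3 defines patient-level improvement with the correct sign for symptoms and for function. A reader might also infer that faster worsening would in practice be reported as effectiveness. That would mean following one word against the endpoint definition and the pivotal-study account, and no decision rule obliges anyone to do so.

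The reply does not remove the contradiction. The sentence is presented as a pre-specification in the statistical section, its promised completion is absent, and the reversals elsewhere make it unsafe to rely on readers to correct it unprompted.

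**Conclusion.** The direction stated in Protocol 9.5.2.3 is wrong by the protocol's own definition and its own account of the pivotal study. It is the only treatment-level patient-reported criterion that carries a direction. The mean-change criterion has none, and SAP 5.2.2 does not supply the effect deferred to it.

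The severity is low. No estimate, interval, test or sample size changes. The effect is confined to how the seven key-symptom time-to-deterioration endpoints are to be interpreted. The reversed rows in the visit-response table and in SAP 4.2.2.2 are separate errors and could change computed results. They matter here because the corrected sentence is right only if the event is a rise in symptom score.

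The conclusion assumes that the intended direction is the one in Protocol 2.3.1.2 and in the endpoint definition. Nothing in the documents offers a rationale for the opposite.

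**What to change.** 1. In Protocol 9.5.2.3, replace *reduce* with *prolong*, and state that benefit in mean symptom score is a decrease from baseline.
2. Carry both directions into SAP 5.2.2. Either state there the effect sought and the reference against which a single-arm result will be judged, or say that these endpoints are descriptive only and drop the protocol's deferral.
3. In the same revision, correct the symptom row of the visit-response table so that a rise of 10 or more is deterioration and a fall of 10 or more is improvement. Make the symptom deterioration and symptom improvement definitions in SAP 4.2.2.2 agree with the Protocol 9.5.2.3 text and with SAP 5.2.2.

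The cost is a few words in the protocol sentence, a line or two in SAP 5.2.2, one table row and two parenthetical definitions in SAP 4.2.2.2. Data collection and sample size are unaffected. Any program already written from the SAP 4.2.2.2 symptom definitions would need checking.

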9.5.2.4 Healthcare resource use

An exploratory health economic analysis of hospital episodes including type of contact (hospitalization, outpatient, or day case), reason, length of stay by ward type (including intensive care unit), procedures, and tests may be undertaken to examine the impact of disease and treatment on resource use to primarily support the economic evaluation of durvalumab + EP. This would include providing descriptive statistics as appropriate, including means, median, and ranges. Costs associated with HCRU use will be quantified by multiplying the natural units of use of each resource by the cost of each resource retrieved from Spanish databases.

9.5.3 Biomarker data

The relationship of exploratory biomarkers to clinical outcomes (including but not restricted to) of PFS, ORR, and OS will be explored.

Summaries and analyses for exploratory biomarkers will be documented in a separate analysis plan and will be reported outside the CSR in a separate report.

9.6 Interim analyses

Not applicable

Appendix A Regulatory, ethical and study oversight considerations

A 1 Regulatory and ethical considerations

This study will be conducted in accordance with the protocol and with the following:

- Consensus ethical principles derived from international guidelines including the Declaration of Helsinki and Council for International Organizations of Medical Sciences (CIOMS) International Ethical Guidelines
- Applicable ICH Good Clinical Practice (GCP) Guidelines
- Applicable laws and regulations
- AstraZeneca will be responsible for obtaining the required authorisations to conduct the study from the concerned Regulatory Authority. This responsibility may be delegated to a CRO but the accountability remains with AstraZeneca.

The protocol, protocol amendments, ICF, Investigator Brochure, and other relevant documents (eg, advertisements) must be submitted to an IRB/IEC by the sponsor and reviewed and approved by the IRB/IEC before the study is initiated.

Any amendments to the protocol will require IRB/IEC approval before implementation of changes made to the study design, except for changes necessary to eliminate an immediate hazard to study patients.

Regulatory Reporting Requirements for SAEs

Prompt notification by the investigator to the sponsor of a SAE is essential so that legal obligations and ethical responsibilities towards the safety of participants and the safety of a study intervention under clinical investigation are met.

The sponsor has a legal responsibility to notify both the local regulatory authority and other regulatory agencies about the safety of a study intervention under clinical investigation. The sponsor will comply with country-specific regulatory requirements relating to safety reporting to the regulatory authority, Institutional Review Boards (IRB)/Independent Ethics Committees (IEC), and investigators.

For all studies except those utilizing medical devices investigator safety reports must be prepared for suspected unexpected serious adverse reactions (SUSAR) according to local regulatory requirements and sponsor policy and forwarded to investigators as necessary.

An investigator who receives an investigator safety report describing a SAE or other specific safety information (eg, summary or listing of SAEs) from the sponsor will review and then file it along with the [Investigator's Brochure or state other documents] and will notify the IRB/IEC, if appropriate according to local requirements.

The study will be performed in accordance with the AstraZeneca policy on Bioethics and Human Biological Samples.

A 2 Financial disclosure

Investigators and sub-investigators will provide the Sponsor with sufficient, accurate financial information as requested to allow the Sponsor to submit complete and accurate financial certification or disclosure statements to the appropriate regulatory authorities. Investigators are responsible for providing information on financial interests during the course of the study and for 1 year after completion of the study.

A 3 Informed consent process

The Investigator or his/her representative will explain the nature of the study to the patient or his/her legally authorized representative and answer all questions regarding the study.

Patients must be informed that their participation is voluntary. Patients or their legally authorized representative will be required to sign a statement of informed consent that meets the requirements local regulations and ICH guidelines, where applicable, and the IRB/IEC or study center.

The medical record must include a statement that written informed consent was obtained before the patient was enrolled in the study and the date the written consent was obtained. The authorized person obtaining the informed consent must also sign the ICF.

Patients must be re-consented to the most current version of the ICF(s) during their participation in the study.

A copy of the ICF(s) must be provided to the patient or the patient's legally authorized representative.

If a patient declines to participate in any voluntary exploratory genetic research component of the study, there will be no penalty or loss of benefit to the patient and he/she will not be excluded from other aspects of the study.

If a patient's partner becomes pregnant during or within 90 days after the last dose of durvalumab, the partner is asked to sign the "Adult Study Informed Consent Form for Pregnant Partners of Study Patients" and provide information about the pregnancy accordingly.

The ICF will contain a separate section that addresses the use of remaining mandatory samples for optional exploratory research. The Investigator or authorized designee will explain to each patient the objectives of the exploratory research. Patients will be told that they are free to refuse to participate and may withdraw their consent at any time and for any reason during the storage period. The patient will give a separate agreement to allow any remaining specimens to be used for exploratory research. Patients who decline to participate in this optional research will indicate this in the ICF. If a patient withdraws consent to the use of donated biological samples, the samples will be disposed of/destroyed, and the action documented. If samples already have been

analyzed at the time of the request, AstraZeneca will not be obliged to destroy the results of this research.

A 4 Data protection

The ICF will incorporate wording that complies with relevant data protection and privacy legislation. In some cases, such wording will be in a separate accompanying document. AstraZeneca will not provide individual genotype results to patients, their family members, their general physician, any insurance company, any employer, or any other third party, unless required to do so by law.

Precautions are taken to preserve confidentiality and prevent genetic data from being linked to the identity of the patient. In exceptional circumstances, however, certain individuals might see both the genetic data and the personal identifiers of a patient. For example, in the case of a medical emergency, an AstraZeneca Physician or an Investigator might know a patient's identity and might also have access to his or her genetic data. Also, regulatory authorities may require access to the relevant files. Even so, the patient's medical information and the genetic files would remain physically separate.

Each Investigator will ensure that all site personnel involved will respect the confidentiality of any information about trial subjects. Management of personal data from subjects participating in the trial, particularly as regards consent, will comply with General Data Protection Regulation (EU) 679/2016 and the Spanish Organic Law 3/2018 of 05th December on the protection of personal data.

Each patient will be assigned a unique identifier by the Sponsor. Any patient records or data sets transferred to the Sponsor will contain only the identifier; patient names or any information which would make the patient identifiable will not be transferred.

The patient must be informed that his/her personal study-related data will be used by the Sponsor in accordance with local data protection law. The level of disclosure must also be explained to the patient.

The patient must be informed that his/her medical records may be examined by Clinical Quality Assurance auditors or other authorized personnel appointed by the Sponsor, by appropriate IRB/IEC members, and by inspectors from regulatory authorities.

A 5 Committees structure

The safety of all AstraZeneca clinical studies is closely monitored on an on-going basis by AstraZeneca representatives in consultation with Patient Safety. Issues identified will be addressed; for instance this could involve amendments to the Clinical Study Protocol and letters to Investigators.

A 6 Dissemination of clinical study data

A description of this clinical study will be available on <http://astrazenecaclinicaltrials.com> and <http://www.clinicaltrials.gov> as will the summary of the *main* study results when they are

available. The clinical study and/or summary of *main* study results may also be available on other websites according to the regulations of the countries in which the *main* study is conducted.

A 7 Data quality assurance

All patient data relating to the study will be recorded on printed or electronic CRF unless transmitted to the Sponsor or designee electronically (eg, laboratory data). The Investigator is responsible for verifying that data entries are accurate and correct by physically or electronically signing the CRF.

The Investigator must maintain accurate documentation (source data) that supports the information entered in the CRF.

The Investigator must permit study-related monitoring, audits, IRB/IEC review, and regulatory agency inspections and provide direct access to source data documents.

The Sponsor or designee is responsible for the data management of this study including quality checking of the data.

Study monitors will perform ongoing source data verification to confirm that data entered into the CRF by authorized site personnel are accurate, complete, and verifiable from source documents; that the safety and rights of patients are being protected; and that the study is being conducted in accordance with the currently approved protocol and any other study agreements, ICH GCP, and all applicable regulatory requirements.

Records and documents, including signed ICFs, pertaining to the conduct of this study must be retained by the Investigator for 25 years after study completion unless local regulations or institutional policies require a longer retention period. No records may be destroyed during the retention period without the written approval of the Sponsor. No records may be transferred to another location or party without written notification to the Sponsor.

A 8 Source documents

Source documents provide evidence for the existence of the patient and substantiate the integrity of the data collected. Source documents are filed at the Investigator's site.

Data reported on the CRF that are transcribed from source documents must be consistent with the source documents or the discrepancies must be explained. The Investigator may need to request previous medical records or transfer records, depending on the study. Also, current medical records must be available.

All information in original records and certified copies of original records of clinical findings, observations, or other activities in a clinical study necessary for the reconstruction and evaluation of the study are defined as source documents. Source data are contained in source documents (original records or certified copies).

A 9 Publication policy

The results of this study may be published or presented at scientific meetings. This allows the Sponsor to protect proprietary information and to provide comments.

The Sponsor will comply with the requirements for publication of study results. In accordance with standard editorial and ethical practice, the Sponsor will generally support publication of multicenter studies only in their entirety and not as individual site data. In this case, a coordinating Investigator will be designated by mutual agreement.

Authorship will be determined by mutual agreement and in line with International Committee of Medical Journal Editors authorship requirements.

A 10 Trial Monitoring and serious breaches

The clinical monitors are employees of APICES, and representatives of the sponsor. As such, they have the obligation to follow the trial closely so that all aspects of the trial are carefully monitored for compliance with applicable government regulations and with ICH E6(R2) guidelines.

The clinical monitors will visit the study sites and Investigators at intervals as defined in the monitoring plan, in addition to maintaining necessary contact through telephone, e-mail, and letter. The clinical monitors will maintain current personal knowledge of the trial through observation, review of trial records and source documentation, and discussion of the conduct of the trial with the study site Investigators and staff.

Serious breaches of the authorised protocol or of the Royal Decree 1090/2015 occurring in Spain must be reported by the sponsor without undue delay and no later than seven calendar days from becoming aware of the breach to the Spanish Agency of Medicines and Medical Devices (AEMPS) and the CEIm.

To this end, a serious breach shall be defined as a breach that may significantly affect the safety and rights of the trial subjects or the reliability and robustness of the data generated in the clinical trial.

Only serious breaches should be notified to the AEMPS and the CEIm, and the breaches that do not constitute a serious breach should not be notified.

Each study site Investigator must document and explain in the subject's source documentation any breaches from the approved protocol and / or the Royal Decree 1090/2015. Investigators may implement a breach to eliminate an immediate hazard to trial subjects without prior IEC informed consent approval, but the breach must be reported to the monitor/CRA within 1 working day. Such incidents will be evaluated for potential safety hazards of the ongoing study, and if deemed appropriate, a protocol amendment will be issued.

The monitor/CRA will document breaches throughout the course of monitoring visits.

